### *Follow-up of SAEs, Unexpected Events, and Related Events*

Any SAEs that are unresolved at the time of the patient's termination from the trial will be followed by the clinical investigator until the events have been resolved, the patient is lost to follow-up, or the adverse event is otherwise explained or has stabilized.

For the safety and adverse events monitoring data, incidents of adverse events will be summarized by event type, grade, and body system. The proportion of patients with AEs will be calculated and presented with a 95% confidence interval.

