#### **7) Study Participant Safety**

Study participants will be evaluated at multiple timepoints across the study: their in-person 3-month and 12-month visits and their 6, 9 and 13-month phone calls. This evaluation includes any adverse events, especially adverse events (AEs) related to AAD treatment. AEs related to dronedarone are defined in the **Safety/Adverse Event Monitoring Plan** section of this protocol.

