#### **9) Left Ventricle (LV) Structural and Functional Changes**

LV structure, or fibrosis (%), will be assessed using native T1 and ECV MRI sequences included in the CMR imaging. LV function will be measured as the ejection fraction (LVEF) and LV strain using cine-MRI sequences performed as part of the CMR protocol (see appendix)

Secondary endpoints will be analyzed at 3 (0-3) and 13-months (0-13) post-ablation and compared between the two trial arms.

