### *Treatment Group (dronedarone [Multaq®])*

Patients randomized to receive dronedarone will receive an initial dose after their cardiac ablation procedure. If a new AAD is initiated, i.e. not dronedarone, the trial drug will be discontinued. If drug discontinuation occurs, the patient will continue to be monitored for fibrosis progression and AA recurrence/AF burden post-ablation. The evaluation of co-primary endpoints as well as all secondary endpoints will continue to be recorded throughout the duration of the trial.

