### *Control Group (Placebo)*

Patients randomized to the control group will receive an initial placebo dose after cardiac ablation. In the case of AA recurrence, initiation of AADs will be left at the discretion of the treating physician, with recommendations to limit the use of AADs to essential cases only and to avoid prescribing amiodarone or dronedarone. In the case of a new AAD initiation, placebo treatment will be discontinued. The patient will continue to be monitored for fibrosis progression and AA recurrence/AF burden post-ablation. The

---

 Please see **Appendix A: Placebo Composition** for more information.

Page 16 of 49

evaluation of co-primary endpoints as well as all secondary endpoints will continue to be recorded throughout the duration of the trial.

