#### *Dronedarone (Multaq®) and Matching Placebo Dose and Dosing Regimen*

Dronedarone or a matched dose of placebo will be administered orally twice a day for 12 months. The placebo used in this trial is a physical match to the drug product. The study participant will be required to document medication regimen adherence on paper or on an electronic drug diary.

The trial drug should be taken after a meal. It should also be taken with a large glass of water (~250 mL) and consumed over as short a time as possible. Study participants should be instructed to swallow the capsules whole and not chew them. Study participants who are randomly assigned to the treatment group will take two 400 mg dronedarone (Multaq®) tablets each day. Those assigned to the control group will take two placebo tablets each day. Please refer to the “**Dose Administration by Group Assignment**” table below for more information.

If the study participant forgets to take the scheduled dose, s/he should not take the dose more than 4 hours after the usual time and should continue treatment the next day. Any missed doses should be skipped altogether and should not be replaced or made up at the next scheduled dosing.

Dose Administration by Group Assignment		
Assigned Group:	Number of Study Participants:	Dose:
Treatment Group	n=165	400 mg dronedarone (Multaq®), taken orally twice a day for 1 year
Control Group	n=165	400 mg of placebo taken orally twice a day for 1 year

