### *Study Duration and Close Out*

This study will span 13 months with the study participant receiving 12 months of study drug plus an additional one month of continuous ECG monitoring. In other words, approximately 13 months will be for follow-up after the last patient has been randomized into a treatment arm.

An additional 6 months is needed for data cleaning and validation, analysis, and other close out activities such as manuscript preparation.

Tulane University ARO may keep trial related information (e.g. biological sample results, ECG readings and reports, MRI scans and reports) for up to 7 years after the end of the clinical trial.

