### **Adverse Events (AEs) and Serious Adverse Events (SAEs)**

An adverse event (AE) is any unforeseen medical occurrence experienced by a patient in the clinical trial. This event can constitute a disease, related signs or symptoms to the investigational drug or study device. All clinical investigators will evaluate and record these events on the appropriate form. Arrhythmias will not require reporting as an AE because the patient will be transmitting ECGs via their ECG device, and these will be reviewed and interpreted by the central monitoring team. A serious adverse event (SAE) is an adverse event that results in death, hospitalization, is life threatening or requires intervention.

For each AE+/SAE, the clinical investigator will record whether an intervention was also required:

- **Intervention-** Surgery or procedure
- **Other treatment-** medication initiation/change, discontinuation
- **None-** no action was taken

In addition, the clinical investigator will also record any clinical outcome of each AE+/SAE:

- Death
- AE resolved or the symptoms/signs that constitute the AE returned to baseline
- AE resolved with permanent sequelae
- Symptoms that constituted the AE are ongoing

Each participating clinical trial site and its investigator has a primary responsibility for the safety of the patients under his or her care. In person visits will occur at 3 and 12-months, and follow-up phone calls/visits will be held at 6, 9-months and towards the end of the clinical trial (Month 13). Clinical investigators or the research team may schedule additional clinic visits according to their standard of

care or as needed to maintain patient safety during the trial. These visits as well as any new or worsening symptoms or events will also be recorded on DACIMA during this time.

All adverse events that occur after randomization will be evaluated throughout the follow-up periods and will be collected and stored on DACIMA.

Serious adverse events (SAE) must be reported in an expedited manner to the IRB and Tulane University ARO, to allow for optimal monitoring of patient safety and care.

Please refer to the Adverse Events & Reporting section for provided timelines on reporting AE, SAE and UP and completing the respective logs.

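### Adverse events are compared only by randomised arm over 0-3 and 0-13 months, with no on-treatment or person-time analysis, although product stops at any new antiarrhythmic drug and at month 12, so an excess on dronedarone may be understated

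*Combined protocol and SAP*

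**What the plan says.** Study Participant Safety is secondary endpoint 7: "This evaluation includes any adverse events, especially adverse events (AEs) related to AAD treatment". The sentence closing the list of secondary endpoints sets the windows and the contrast: "Secondary endpoints will be analyzed at 3 (0-3) and 13-months (0-13) post-ablation and compared between the two trial arms". Collection does not depend on whether product is still being taken: "All adverse events that occur after randomization will be evaluated throughout the follow-up periods" (Adverse Events and Serious Adverse Events section). The summary measure is in the section on follow-up of SAEs: "The proportion of patients with AEs will be calculated and presented with a 95% confidence interval". That sentence names neither arms nor a window, so the between-arm comparison rests on the secondary endpoint text.

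Exposure can end early in either arm. For dronedarone: "If a new AAD is initiated, i.e. not dronedarone, the trial drug will be discontinued". For control: "In the case of a new AAD initiation, placebo treatment will be discontinued". In both cases the patient stays in follow-up. Planned exposure is also shorter than follow-up: "Dronedarone or a matched dose of placebo will be administered orally twice a day for 12 months", while Study Duration and Close Out describes participants "receiving 12 months of study drug plus an additional one month of continuous ECG monitoring".

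The plan defines no safety set, treatment-emergent definition, on-treatment window or exposure-adjusted rate for AEs. Intention-to-treat is specified for primary efficacy. The one as-treated element, a per-protocol robustness analysis, is in section C on the co-primary endpoints and is not tied to AEs. Section D makes all secondary analyses descriptive.

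**The concern.** A by-arm AE count over all follow-up answers what happens to patients assigned to each strategy. It does not isolate what happens while patients take dronedarone rather than placebo, and endpoint 7 puts its emphasis on events related to AAD treatment. Once a control patient starts another AAD, any AE on that drug counts as a control event. Once a dronedarone patient stops, later time and events still count under dronedarone.

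Rescue in control is likely to be the more common, because the sample-size section expects 50% of controls to recur and a 33% relative reduction on dronedarone. The Concomitant Medications section lists Class I and III antiarrhythmics among drugs that prolong QT and might raise torsade risk. The Background says dronedarone carries fewer non-cardiovascular risks and less ventricular pro-arrhythmia than other AADs. On that text, rescue drugs cannot be assumed harmless. For efficacy, dilution between arms is conservative. For harm it works the other way, by drawing the arms together.

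**Working it through.** **The plan's own figures.** The documents give no AE rate, switching rate or AE power. The recurrence inputs can be checked. Dronedarone recurrence = 0.50 × (1 − 0.33) = 0.335. Events = 165 × (0.50 + 0.335) = 137.8, i.e. the stated 138. HR = ln(0.665)/ln(0.5) = 0.589. Freedman power = Φ(√138 × (1 − 0.589)/(1 + 0.589) − 1.96) = 86.0%, as stated. This confirms the recurrence inputs but says nothing about AEs.

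**Illustrative model (assumptions, not document figures).** Recurrence hazards are constant and start at month 0. A share s of recurrences leads to a new AAD, which stops product and continues to month 13. Monthly AE rates, relative to placebo, are: on placebo or off drug 1; on dronedarone 2.0; on a rescue AAD k. Dropout and stopping for other reasons are ignored.

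For recurrence probability p:
- switching hazard h = −s × ln(1 − p)/12
- months on product = (1 − e^(−12h))/h
- months off drug after month 12 without a switch = e^(−12h)
- months on rescue AAD = 13 minus the two above

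| s | Control: product / off drug / rescue | Dronedarone: product / off drug / rescue |
|---|---|---|
| 25% | 11.02 / 0.84 / 1.14 | 11.41 / 0.90 / 0.69 |
| 50% | 10.14 / 0.71 / 2.15 | 10.86 / 0.82 / 1.33 |
| 100% | 8.66 / 0.50 / 3.84 | 9.85 / 0.67 / 2.48 |

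Rescue time is 9-30% of the 13 months in control and 5-19% on dronedarone.

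All-follow-up rate ratio = (2 × product + off drug + k × rescue, dronedarone) / (product + off drug + k × rescue, control):
- s = 25%, k = 1: 24.41/13.00 = 1.88
- s = 50%, k = 2: 25.18/15.15 = 1.66
- s = 100%, k = 3: 27.82/20.69 = 1.34

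The rate difference is 88% of the on-treatment difference in the first case and 55% in the last.

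**Post-dosing month alone.** With no switching, the ratio is (12 × 2 + 1)/13 = 25/13 = 1.92. That month is 1/13 = 7.7% of the window. Rescue AADs are the larger influence.

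**Direction.** With a true ratio of 1.0, s = 50-100% and k = 2-3, the by-arm ratio is 0.95 to 0.87, so dronedarone would look safer than it is. The direction can reverse. If dronedarone patients switched more (recurrence set at 70% against 50%, s = 80%, k = 4), a true ratio of 1.3 shows as 1.33. That needs recurrence to run against the plan's own expectation.

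**Rates and proportions.** The planned statistic is a proportion of patients, which compresses ratios even without switching. If 10% of placebo patients have an AE in 12 months (assumed), a rate ratio of 2.0 held for all 13 months gives (1 − 0.9^(26/12))/(1 − 0.9^(13/12)) = 0.204/0.108 = 1.89. With 30% it gives 0.538/0.320 = 1.68. Averaging 1 − exp(−cumulative hazard) over switch times in the model above, the proportion ratio runs from 1.79 to 1.32 (10%) and from 1.61 to 1.27 (30%). The rate ratios of 1.88 to 1.34 therefore describe dilution of the underlying contrast and do not forecast the planned table.

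**The case against.** Comparing AEs as randomised over all follow-up is a legitimate treatment-policy summary. It keeps the randomised comparison and catches harms that appear after stopping, which matters because the product insert lists liver and lung injury. An on-treatment table censors at non-random stopping. This stands, and it is why the on-treatment table should be added beside the by-arm table and should not replace it.

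A reader might infer that dronedarone's excess risk is understated as a matter of fact. The documents do not support that. Product stops at a new AAD in both arms, so rescue-AAD events also count as dronedarone events. Recurrence is not the same as AAD initiation: Study Design and the Control Group section ask physicians to limit AADs to essential cases and to avoid amiodarone and dronedarone. No AE or switching rate is given.

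A reader might also infer that the boxed-warning risks of death and stroke would be hidden. The Dronedarone subsection of the adverse event section says those risks come from heart-failure and permanent-AF patients, and that these groups are not enrolled. The warning does not carry this point.

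The 0-3 month comparison contains no post-dosing month and leaves less time for rescue to accumulate. It is less exposed but not immune, because an AAD may be started in the blanking period.

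Finally, secondary analyses are descriptive and the DSMB reviews all AEs at its meetings. That limits the consequence but does not remove it: a descriptive table is still the trial's reported safety comparison.

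**Conclusion.** The gap is real: AEs are compared by arm over 0-3 and 0-13 months as a crude proportion, and no planned analysis separates time on trial product from time on a rescue AAD or off drug. Under the plan's recurrence assumptions the likely effect is to understate an excess on dronedarone, so *may be understated* is as far as the documents go. The size is unknown. The range of 1.88 to 1.34 for a true rate ratio of 2.0 rests wholly on the assumed ratio, the assumed 25-100% of recurrences given a new AAD, and the assumed rescue-AAD rate of 1-3 times placebo. The post-dosing month is a minor part. The defect is a missing complementary analysis; the by-arm analysis itself is not wrong. It should be put right, but it does not threaten the primary conclusions.

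**What to change.** In the AE summary text and the closing sentence of the secondary endpoints, keep the 0-3 and 0-13 month as-randomised tables and prespecify, beside them:

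1. A safety set of patients who took at least one dose.
2. An on-treatment comparison by arm, counting AEs with onset from first dose to last dose of trial product plus a stated lag. Five times the upper 19 h elimination half-life in Appendix C is 95 h, about 4 days. Appendix C also describes an active metabolite without giving its half-life, so the lag should be labelled an assumption.
3. Both measures in that table: patients with at least one AE, and events per person-time.
4. A separate tabulation of AEs with onset after a new AAD, by arm.

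Most of the data are already planned: AE onset dates (AE data collection procedures), AAD initiation (primary endpoint 1b and secondary endpoint 1), and the drug diary and accountability records. The sponsor should confirm that the last-dose date and the new-AAD start date are captured as dates.

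The cost is one more set of tables. The on-treatment table is not a randomised comparison and can miss slow-onset harms, so neither table should be shown without the other.

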## **Data Safety and Monitoring**

### ***Data Safety Monitoring Board (DSMB)***

The study will be formally monitored by a Data and Safety Monitoring Board (DSMB). This is an independent board that will have a charter. They will monitor safety data on a regular basis to ensure the continuing safety of the patients involved in this clinical trial. Enrollment will not be paused during these safety reviews.

The DSMB can also recommend modifications to the data management and monitoring procedures in the trial or to the protocol. Every effort will be made to reach a consensus within the DSMB and with the Principal Investigator. In case of disagreement on recommended modifications, the Steering Committee will decide. The DSMB will meet at least two times a year at the discretion of the Chairperson. An emergency meeting may be called at any time throughout the trial should an unforeseen problem arise. The DSMB's full responsibilities, authorities, and procedures will be documented in the DSMB Charter.

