#### ***Atrial Arrhythmia (AA) Recurrence***

The rate limiting factor in the required sample size is AA recurrence (atrial fibrillation, atrial flutter, atrial tachycardia). AA recurrence is defined as a one instance, continuous >30 second strip reading on either 12-lead ECG, Holter monitor or study devices (including during the blanking period)

AA recurrence will be based on the following assumptions:

- 50% of patients in the control group will have AA recurrence in 1-year, post-ablation (including during the blanking period) and,
- the relative reduction of AF recurrence will be by 33% in the dronedarone group compared to the control group and,
- 20% of subjects could be lost during the follow-up periods and,
- 2-sided  $\alpha=0.05$ .

The EDORA trial will have a total of 330 patients participating, thus, 165 in each trial arm. Therefore, a calculated total of 138 AF recurrences will have 86% power to detect the group differences.

The study will be defined as successful if the hypotheses for both co-primary endpoints are positive, i.e., rejecting the null hypothesis. Therefore, in terms of overall type I error of the study, the sample size calculation does not need to adjust for the multiplicity. However, the type II error, i.e., the power for each individual test needs to be adjusted in this case to achieve the overall power of the study. For the endpoint of atrial fibrosis progression, given that 330 patients will be recruited, we have almost 100% power to detect the expected difference. For AF recurrence, the study will have at least 85% power. Therefore, for the two co-primary endpoints, the study will have at least 85% overall power for a positive outcome, i.e., the study is powered to detect the difference in both atrial fibrosis progression and AF recurrence between the two arms.

Most studies evaluating the effects of AAD after ablation started their monitoring after the 3-month blanking period. Our trial will start assessing for the primary endpoint of AF recurrence on the day of discharge, and so we expect a significantly higher event rate. A few recent studies reporting recurrence data during the first three months after ablation such as, the AMIO-CAT study showed a 53% AF recurrence rate after ablation in a placebo group and AF recurrence at 6 months was 48%. In the EAST-AF study, randomizing paroxysmal and persistent AF patients to short term AAD use vs control, the rate

Page 34 of 49

Version 4.0:  
Revision Date: April 27th, 2022

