#### **D. Analysis of the secondary endpoints**

The secondary endpoints will be analyzed only as supporting evidence. There will be no intention to claim treatment benefits for the listed secondary endpoints. As such, data analysis for secondary endpoints are purely for descriptive purposes and not for drawing inferences.

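### Safety is to be compared between arms, but the only stated interval is for a single AE proportion; no between-arm difference in harm is required

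*Combined protocol and SAP*

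**What the plan says.** Secondary endpoint 7, Study Participant Safety, covers adverse events at the scheduled contacts: "This evaluation includes any adverse events, especially adverse events (AEs) related to AAD treatment". The paragraph that closes the list of secondary endpoints applies to all of them: "Secondary endpoints will be analyzed at 3 (0-3) and 13-months (0-13) post-ablation and compared between the two trial arms". It names no effect measure or method.

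The analysis of adverse events is in Follow-up of SAEs, Unexpected Events, and Related Events. It has two parts. First, "incidents of adverse events will be summarized by event type, grade, and body system". Second, "The proportion of patients with AEs will be calculated and presented with a 95% confidence interval". Neither sentence mentions treatment arm, a risk difference, a ratio or a test.

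Section D of the statistical methods, on the secondary endpoints, explains that no treatment benefit will be claimed from them and concludes that "data analysis for secondary endpoints are purely for descriptive purposes and not for drawing inferences". It makes no exception for endpoint 7.

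For benefit the plan is more specific. Section C (Analysis of AF Recurrence) promises a hazard ratio between the groups with its 95% CI.

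**The concern.** Three statements do not fit together. One promises a between-arm comparison of safety. The second supplies an interval that answers a different question: how precisely one proportion is known. The third restricts interpretation of every secondary endpoint, on grounds that apply to efficacy claims and not to harms.

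The trial declares success on the two co-primary endpoints. A positive result would have to be weighed against the harms that the protocol itself lists for dronedarone (pulmonary, thyroid, hepatic, bradycardia, QT prolongation, gastrointestinal, neurological, chest pain, heart failure, creatinine). As written, the reader of the final report is assured of a between-arm estimate with uncertainty for recurrence, and of no such estimate for harm. A reader given only two separate intervals is likely to compare them by eye, which is a poor guide to the difference.

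**Working it through.** **No figure to reproduce.** The documents state no adverse event rate, safety sample size or safety power. All event counts and rates below are assumptions. From the documents: 165 patients per arm (sample size section on AA recurrence), a 95% interval level, and 20% possible loss, which leaves 0.8 × 165 = 132 per arm.

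**Step 1. The interval the plan states.** The plan does not name a method for the single proportion; I use Wilson:

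(p + z²/2n ± z√[p(1−p)/n + z²/4n²]) / (1 + z²/n), with z = 1.96.

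For an event in 10 of 165 on dronedarone and 2 of 165 on placebo:
- Dronedarone: p = 6.1%. Centre (0.0606 + 0.0116)/1.0233 = 0.0706; half-width 1.96 × √(0.000345 + 0.000035)/1.0233 = 0.0374. Interval 3.3 to 10.8%.
- Placebo: p = 1.2%. Interval 0.3 to 4.3%.

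The two intervals overlap between 3.3% and 4.3%.

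**Step 2. The interval the promised comparison needs.** Newcombe's interval for d = p₁ − p₀ is built from the same Wilson limits (l, u):

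lower = d − √[(p₁ − l₁)² + (u₀ − p₀)²]; upper = d + √[(u₁ − p₁)² + (p₀ − l₀)²].

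- d = 0.0606 − 0.0121 = 0.0485 (4.8 points)
- lower = 0.0485 − √(0.0274² + 0.0310²) = 0.0485 − 0.0414 = 0.0071
- upper = 0.0485 + √(0.0474² + 0.0088²) = 0.0485 + 0.0482 = 0.0967

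The difference is 4.8 points (0.7 to 9.7), which excludes zero; Fisher's exact p = 0.035.

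**Step 3. Other illustrative counts, 165 per arm.**

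| Dronedarone v placebo | Dronedarone 95% CI | Placebo 95% CI | Difference, points (95% CI) |
|---|---|---|---|
| 10 v 2 | 3.3 to 10.8% | 0.3 to 4.3% | 4.8 (0.7 to 9.7) |
| 15 v 5 | 5.6 to 14.5% | 1.3 to 6.9% | 6.1 (0.8 to 11.7) |
| 50 v 33 | 23.8 to 37.7% | 14.6 to 26.8% | 10.3 (0.9 to 19.5) |

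In each row the separate intervals overlap and the interval for the difference excludes zero.

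**Step 4. Is this peculiar to the chosen counts?** Enumerating all outcomes under two independent binomials gives the probability that each display shows a true excess:

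| Assumed true rates, placebo v dronedarone | Difference CI above 0 (165 / 132 per arm) | Separate CIs do not overlap (165 / 132 per arm) |
|---|---|---|
| 2% v 6% | 44% / 34% | 14% / 11% |
| 5% v 10% | 40% / 32% | 13% / 10% |
| 10% v 15% | 28% / 23% | 8% / 6% |
| 10% v 20% | 73% / 63% | 41% / 31% |
| 20% v 30% | 56% / 47% | 25% / 19% |

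The interval for the difference is the more informative display throughout. Even so, its chance of excluding zero runs only from 23% to 73% in this range.

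**The case against.** The strongest reply is that the plan leaves room for sound safety reporting and nothing in it conceals harm. Much of this stands.

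- A reader might infer that the AE proportion will be pooled over arms. The documents do not support that: endpoint 7 falls under the statement that secondary endpoints are compared between arms, so by-arm figures are the natural reading even though the AE section does not say so.
- A reader might infer that the single proportion is the whole safety analysis. It is not: events are also summarised by type, grade and body system, and the secondary endpoints have two analysis windows.
- A reader might infer that a real excess would be reported as no finding. Section D limits claims; it does not suppress results. A table showing 10/165 and 2/165 discloses the excess, and anyone can compute the difference. Of the DSMB the protocol says "They will monitor safety data on a regular basis to ensure the continuing safety of the patients involved in this clinical trial", and the board also reviews all adverse events at its meetings.
- No section says arms will be judged by whether their intervals overlap. Steps 3 and 4 show what a reader loses by being given only separate intervals; they do not test a rule that the plan adopts.
- The counts in Step 3 are assumed and lie close to the boundary, where the two displays disagree most.
- Reporting many unadjusted intervals has a price. With about ten categories, and assuming independence and no true effect, the chance that at least one excludes zero is 1 − 0.95¹⁰ = 40%.

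What remains is more than a missing detail. The one interval the plan states is the wrong one for the comparison it promises. DSMB monitoring during the trial does not define the comparison in the final report. The no-inference clause reaches harms for a reason that does not apply to them.

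**Conclusion.** The point holds in a limited form. The plan commits to comparing safety between arms but requires no estimate of the between-arm difference in harm, and its only stated safety interval does not provide one. The wording of Section D also discourages interpreting such a difference. The documents do not support the stronger conclusion that an excess on dronedarone would be hidden or dismissed.

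The size can only be illustrated, because the documents give no adverse event rates. At 165 per arm and the assumed rates in Step 4, a true excess shows in 28% to 73% of trials through the interval for the difference, against 8% to 41% through separation of the arm intervals. These figures assume independent binomial counts, Wilson and Newcombe intervals, and every randomised patient in the denominator; with 132 per arm both ranges are lower. Power for modest harms stays low under either display, so the interval should be read as estimation. An interval that includes zero would not establish safety.

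**What to change.** **In Follow-up of SAEs, Unexpected Events, and Related Events:** state that adverse events are reported by arm, giving the number and percent of patients with any AE, any SAE, and each category listed for dronedarone in the section on trial-related adverse events. Add the between-arm risk difference with its 95% CI (for example Newcombe) for each. Label these as estimates without multiplicity adjustment.

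**In Section D:** add that the clause concerns claims of benefit and does not limit the estimation and reporting of between-arm differences in harm. There is no need to turn safety into a tested hypothesis.

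**Cost:** one column in the AE tables and two or three sentences. No new data, visits or patients are needed. Across many categories some intervals will exclude zero by chance, which the label discloses, and wide intervals for uncommon events will remain.
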